5 PROCEDURES

5.1 Study procedures.

Using lay language, provide a complete description of the study procedures, including the sequence, intervention or manipulation (if any), drug dosing information (if any), use of records, time required, and setting/location. If it is available: Upload a study flow sheet or table to [Zipline](#).

For studies comparing standards of care: It is important to accurately identify the research procedures. See UW IRB [POLICY: Risks of Harm from Standard Care](#) and the draft guidance from the federal Office of Human Research Protections, ["Guidance on Disclosing Reasonably Foreseeable Risks in Research Evaluating Standards of Care"](#); October 20, 2014.

This quality improvement research study is designed in two phases, each phase is done over a 3-month period for a total study duration of 6 months. The SCCA study team will be enrolling eligible OMC providers who will handle all patient interaction and communication.

Phase 1: The first phase does not involve intervention; OMC will be following their existing processes. OMC will gather identified data on the patient's clinic diagnosis and stage, pathology report features, and treatment options for patients with the above diagnose and offer patients the option to fill out a standardized Family History Questionnaire (FHQ) on the day of their initial visit if they decide to do so. The FHQ will be offered as part of clinical care up to the discretion of the OMC providers. OMC will also gather de-identified data on the number of patients seen with a diagnosis of breast, ovarian, prostate, colon, and pancreatic cancer. The above data will then be sent to the study's research coordinator at SCCA (through secure email) which will be stored in a secured J-Drive folder within the SCCA network. The research coordinator will randomly assign all identified patient data to a unique participant ID before distributing to SCCA subject matter experts (cancer geneticist and/or genetic counselor) for review. From OMC's collected data, SCCA subject matter experts will measure how many patients met NCCN criteria for testing how many patients were referred to genetic counseling and how many either had a test online or were seen at UWMC and the SCCA for a genetic evaluation.

Phase 2: The second phase involves a tiered intervention in which SCCA subject matter experts will coach the OMC providers to provide guidance on providing genetic counseling and testing to their patients. Involvement in this study does not dictate how the OMC providers carry out clinical care, so it is up to the OMC providers to decide whether or not to implement the coaching in their practice. First, patients and their families fill out the standardized FHQ before their initial appointment, which will be sent via email by the team at OMC. OMC will gather the same patient information described in Phase 1 which will then be sent directly to the study's research coordinator at SCCA, where the research coordinator will follow the same data storage, participant ID assignment, and distribution processes as in Phase 1. SCCA subject matter experts would then review this information with the OMC providers at bi-monthly virtual conferences before patients come for their initial visit at OMC. For patients who meet NCCN criteria, the oncology team at OMC would include in their initial visit workflow to discuss importance of cancer risk assessment and offer genetic testing. For the patients with a more complicated history, the OMC team would offer a referral to the SCCA for a complete cancer risk assessment evaluation.

At the end of phase 2, SCCA subject matter experts will measure how many patients met NCCN criteria for testing how many patients were referred to genetic counseling and how many either had a test online or were seen at UWMC and the SCCA for a genetic evaluation. This data will then be compared with phase 1 data to measure the effectiveness of SCCA's coaching for OMC's providers as well as quality improvement of their processes.

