a.3. Explain which results will not be offered to subjects and provide the rationale for not offering these results.

Reasons not to offer the results might include:

- *There are serious questions regarding validity or reliability*
- *Returning the results has the potential to cause bias*
- *There are insufficient resources to communicate the results effectively and appropriately*
- *Knowledge of the result could cause psychosocial harm to subjects*

b. What is the plan (if any) for offering subjects any results that are not clinically actionable?

Examples: non-actionable genetic results, clinical tests in the normal range, experimental and/or uncertain results.

	No
	Yes

→ If yes, explain which results will be offered to subjects and provide the rationale for offering these results.

c. Describe the validity and reliability of any results that will be offered to subjects.

The IRB will consider evidence of validity such as studies demonstrating diagnostic, prognostic, or predictive value, use of confirmatory testing, and quality management systems.

The results that will be offered to the OMC provider subjects will be reliable due to the consistent, uniform processes in data collection and recommendation that will be followed throughout the entire course of this study. The results will be valid because the reporting of the numbers of patients meeting criteria, referrals for genetic counseling/testing, completed genetics appointments, and genetic testing results, will be recorded and tracked by the same research coordinator.

d. Describe the process for communicating results to subjects and facilitating understanding of the results. In the description, include who will approach the participant with regard to the offer of results, who will communicate the result (if different), the circumstances, timing, and communication methods that will be used.

Results will be communicated to the OMC provider subjects at the end of phase 1 and phase 2. The SCCA study team and subjects will meet to discuss the number of patients seen who were eligible for genetic testing, number of those patients who were referred for genetic counseling/testing, the number of those patients who complete a genetics appointment, and the number of those patients who chose to undergo genetic testing. The OMC provider subjects will also be sent this data for their review in order to assess their current clinic processes.

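### Completed tests and genetics visits are counted when Phase 2 ends, so patients first seen late have little or no follow-up, and the phase comparison mixes speed with uptake

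*Protocol*

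**What the plan says.** Section 5.1 sets the calendar: "each phase is done over a 3-month period for a total study duration of 6 months". The outcomes are how many patients met NCCN criteria, how many were referred, and "how many either had a test online or were seen at UWMC and the SCCA for a genetic evaluation". For Phase 2 the timing is explicit: "At the end of phase 2, SCCA subject matter experts will measure how many patients met NCCN criteria", followed by the referral and completion counts. The purpose is explicit too: "This data will then be compared with phase 1 data to measure the effectiveness of" the coaching.

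Section 5.1 gives no count date for Phase 1. The nearest statement is in section 10.10.d: "Results will be communicated to the OMC provider subjects at the end of phase 1 and phase 2". The results listed there include completed genetics appointments and patients who chose testing. Section 10.10.c adds that "completed genetics appointments, and genetic testing results, will be recorded and tracked by the same research coordinator".

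The route to testing differs by phase. Phase 1 follows existing processes. In Phase 2, for patients who meet criteria, "the oncology team at OMC would include in their initial visit workflow to discuss importance of cancer risk assessment and offer genetic testing"; for more complicated histories, "the OMC team would offer a referral to the SCCA for a complete cancer risk assessment evaluation". The protocol gives no per-patient follow-up window, no early close of entry within a phase and no later chart review.

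**The concern.** A completed genetics visit, and any test not done at the initial visit, happens some time after the patient is first seen. When the count is tied to a calendar date, follow-up runs from a full three months for the first patient to almost none for the last. A late patient who completes the following week is recorded as not completing.

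This touches aim 2 in section 1.5 (uptake of testing) and the comparison meant to show whether coaching works. Coaching changes the route to testing, so it may change how fast a test or visit happens as well as whether it happens. A fixed cut-off cannot separate the two. Aim 3, on outcomes after test results, lies later still.

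**Working it through.** **Duration.** 3 + 3 = 6 months, as stated. No time is left after Phase 2.

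**Inputs.** From the protocol: 3-month phases (taken as 91 days) and at most 60 patients per phase (section 2.7). Assumed, because the protocol gives none: delay from initial visit to completion, true uptake, and entry pattern (uniform unless stated).

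**1. Share of completions counted.** With fixed delay D, uniform entry over E days and a count at day 91, c = min(1, (91 − D)/E).

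| Delay (days) | Missed, E = 91 | Missed, E = 56 |
|---|---|---|
| 7 | 7/91 = 8% | 0% |
| 14 | 14/91 = 15% | 0% |
| 30 | 30/91 = 33% | 0% |
| 45 | 45/91 = 49% | 1 − 46/56 = 18% |

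The E = 56 column supposes that the 60-patient maximum is reached by day 56.

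**2. Both phases cut at their own end, equal 30-day delays.** c = 61/91 = 0.670. True uptake of 20% and 40% is observed as 13.4% and 26.8%. The ratio stays 2.0; the difference falls from 20 to 13.4 points.

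**3. Same cuts, unequal delays, equal true uptake u.** Spurious difference (Phase 2 minus Phase 1) = u × (c2 − c1). With 30 days in Phase 1 and 14 in Phase 2, c2 − c1 = 77/91 − 61/91 = 0.176. That gives +3.5, +7.0 and +10.5 points at u = 20%, 40% and 60%. Swapping the delays reverses the signs.

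**4. Same cuts, equal 30-day delays, unequal entry (deliberately extreme).** If entry declines linearly to zero in Phase 1, c1 = 1 − (30/91)² = 0.891. If it rises linearly from zero in Phase 2, c2 = (61/91)² = 0.449. At 40% true uptake in both, 35.7% against 18.0% is observed.

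**5. Phase 1 charts read at month 6 instead.** Each Phase 1 patient then has 91 days more follow-up than the corresponding Phase 2 patient. With an equal 30-day delay and 40% uptake, Phase 1 shows 40% and Phase 2 shows 0.40 × 0.670 = 26.8%, a spurious −13.2 points.

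**6. How long a per-patient window must be.** Take exponential delays with means of 30 days (Phase 1) and 14 days (Phase 2), and 40% true uptake in both. At an end-of-phase count, c = 1 − (m/91)(1 − exp(−91/m)). With a window of W days from the initial visit, c = 1 − exp(−W/m).

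| Rule | Phase 1 | Phase 2 | Spurious difference |
|---|---|---|---|
| End of phase | 69% | 85% | +6.4 points |
| W = 14 | 37% | 63% | +10.4 |
| W = 30 | 63% | 88% | +10.0 |
| W = 60 | 86% | 99% | +4.9 |
| W = 90 | 95% | 99.8% | +1.9 |

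A window removes differences in entry pattern. It removes differences in delay only if it is long enough for most completions. With fixed delays of 30 and 14 days, a 14-day window would capture none of Phase 1 and all of Phase 2 (+40 points), while a window of 30 days or more would remove the bias.

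**The case against.** The strongest reply is that every size above is assumed and that some plausible cases show no loss: same-day testing, or the 60-patient maximum reached early. That is correct. Testing in particular may often be same-day in Phase 2, where it is offered at the initial visit. Section 10.1 refers to follow-up visits for reviewing results, which shows that results come later, not that the test does. The delay is firmer for completed genetics visits than for tests.

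It can also be said that ascertainment windows belong in an analysis plan, which is not shown, and that this is a six-provider pilot. But study duration and the time of the Phase 2 count are fixed in section 5.1 itself, and measuring uptake needs follow-up whatever the study's size.

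Three stronger readings are tempting, and the documents do not support them:

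- **That coaching will look better than it is.** An offer at the initial visit could speed completion in Phase 2, but the referral tier to SCCA could slow it. The direction is open.
- **That Phase 1 is cut at the end of Phase 1.** Section 10.10.d describes feedback to providers, not a data cut. The alternative, reading Phase 1 at month 6, is no safer (step 5).
- **That late events are lost for good.** Section 5.5 draws clinic outcomes from charts and section 5.6.c keeps a link between patient and participant ID, so they could be abstracted later. The plan as written simply does not count them.

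**Conclusion.** The concern holds for completed genetics visits and for tests not done at the initial visit. Followed as written, the plan understates completed uptake whenever such events fall after the count. If both phases are cut at their own end, equal delays and entry patterns protect the ratio but shrink a true percentage-point difference. If delays or entry patterns differ, or if Phase 1 is read later than Phase 2, the comparison itself is biased. Differing delays are plausible because Phase 2 changes the route to testing.

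That late entrants have little or no follow-up comes from the protocol's own calendar. The size does not: the illustrations run from 0% to 49% of completions missed, on assumed delays and entry. The number meeting NCCN criteria is unaffected and referrals are little affected, so a reader should not infer that the whole phase comparison fails.

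**What to change.** Amend section 5.1 before Phase 1 starts:

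1. Assign each patient to the phase of the initial visit.
2. Count completed tests and genetics visits within one identical window from that visit in both phases. Set the window in advance, long enough for most completions: for example 60 to 90 days. A window of 14 to 30 days can enlarge the bias when delays differ (step 6).
3. Move the Phase 2 chart cut-off, and the comparison, past the end of Phase 2 by that window.
4. Report Phase 1 completions before and after the start of coaching separately.
5. Show the already planned referral counts alongside, as they are little affected by the cut-off.

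**Cost.** Read-out moves from about day 182 to day 242 (182 + 60) or day 272 (182 + 90). Initial-visit and completion dates must be abstracted from charts. No patients or study visits are added.

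**Downside.** With uniform entry, 60/91 = 66% of Phase 1 windows (60 days) or 90/91 = 99% (90 days) run into the coaching period, with the same providers. Those patients' initial visits came before coaching, which limits but does not remove the overlap; item 4 makes it visible. Restricting the analysis to patients whose window closes within their own phase would avoid it, but would keep only about 34% (60 days) or 1% (90 days) of entrants.

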The OMC provider subjects will be given detailed instructions (both written and verbal) on how to collect relevant patient data and send electronically to the study's research coordinator (via secure email). Once received by the study's research coordinator, the data will be stored in a secured J-Drive folder within the SCCA network. The research coordinator will randomly assign all identified patient data to a unique participant ID before distributing to SCCA subject matter experts (cancer geneticist and/or genetic counselor) for review. For the bi-monthly conference meetings in which the SCCA subject matter experts review patients' medical records, the study's research coordinator will order the patients for discussion (OMC providers will receive the meeting agendas that lists the patient discussion order which will include patient PHI. SCCA subject matter experts will also receive meeting agendas that lists the same patient discussion order but will only have access to the unique participant ID and no PHI).

10.7 Un-blinding. If this is a double-blinded or single-blinded study in which the participant and/or relevant study team members do not know the group to which the participant is assigned: describe the circumstances under which un-blinding would be necessary, and to whom the un-blinded information would be provided.

N/A. This is not a double-blinded or single-blinded study.

10.8 Withdrawal of participants. If applicable, describe the anticipated circumstances under which participants will be withdrawn from the research without their consent. Also, describe any procedures for orderly withdrawal of a participant, regardless of the reason, including whether it will involve partial withdrawal from procedures and any intervention but continued data collection or long-term follow-up.

10.9 Anticipated direct benefits to participants. If there are any direct research-related benefits that some or all individual participants are likely to experience from taking part in the research, describe them below:

Do not include benefits to society or others, and do not include subject payment (if any). Examples: medical benefits such as laboratory tests (if subjects receive the results); psychological resources made available to participants; training or education that is provided.

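### The coaching experts count both who met NCCN criteria and who was referred, in no stated order, and for Phase 2 the protocol does not say which eligibility determination is the denominator

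*Protocol*

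**What the plan says.** **Phase 1 (section 5.1).** Working from the data that OMC collects, "SCCA subject matter experts will measure how many patients met NCCN criteria for testing how many patients were referred to genetic counseling". Eligibility and referral are counted by the same people, in one sentence, from one body of data. No order, checklist or lock is described.

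**Phase 2 (section 5.1).** The same group delivers the intervention: "SCCA subject matter experts will coach the OMC providers to provide guidance on providing genetic counseling and testing to their patients". They look at each patient early: "SCCA subject matter experts would then review this information with the OMC providers at bi-monthly virtual conferences before patients come for their initial visit". That review matters for care, because "For patients who meet NCCN criteria, the oncology team at OMC would include in their initial visit workflow" a discussion of risk and an offer of testing. The count itself comes later: "At the end of phase 2, SCCA subject matter experts will measure how many patients met NCCN criteria for testing", alongside the referral count. The result is compared with Phase 1 to judge how well the coaching worked.

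**Reporting (section 10.10.d).** The planned results are the number eligible and then how many of those were referred. Eligibility is therefore the denominator.

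**Safeguards.** Section 9.6.b says that the experts receive de-identified information. Section 10.10.c rests validity on the counts, which "will be recorded and tracked by the same research coordinator". Section 10.7 answers the un-blinding question with "This is not a double-blinded or single-blinded study".

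**The concern.** A rate of referral among eligible patients can rise because more patients are referred or because fewer are called eligible. Here the people who decide who is eligible also deliver the coaching and count the referrals. Nothing in section 5.1 requires eligibility to be settled before referral is known.

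Clear cases leave little room for this. Borderline family histories or pathology findings leave more, and section 5.1 itself foresees patients with complicated histories. If such patients are classified once referral is known, the rate can move with no change in practice at Olympic Medical Center (OMC). With at most 60 patients listed per phase in section 2.7, a few reclassified patients would be visible in the comparison.

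**Working it through.** The protocol states no eligibility share, referral rate, effect size or power, and 60 per phase is a maximum without derivation. There is no figure to reproduce. The check is a reading of the text, followed by an illustration on assumed counts.

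**Step 1. When eligibility is judged, and what is known then.**
- Phase 1: judged by the experts from OMC's data at an unstated time, and counted together with referrals.
- Phase 2, first look: at the conference before the initial visit. A referral made at that visit does not exist yet, so this judgement cannot respond to it.
- Phase 2, count: at the end of the phase, together with referrals, which are by then known. If this is a tally of recorded pre-visit judgements, it cannot respond to referral. If it is a fresh judgement, it can. The text fits both, and nothing requires the pre-visit judgement to be recorded.

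**Step 2. What the experts see in Phase 1.** The patient-level items that section 5.1 has coded and distributed are diagnosis and stage, pathology, treatment options and the family history questionnaire. Section 5.5 places referral status under clinic outcomes data drawn from charts. The protocol therefore does not say that referral sits in the packet. But the same experts count referrals from the collected data, and no step keeps the two apart.

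**Step 3. Illustration (all counts assumed).** Rate = referred / judged eligible. Each phase has 60 patients: 24 clearly eligible, 12 borderline, 11 referred (9 clear, 2 borderline). Practice does not change between phases.
- Phase 1, all borderline patients counted: 11/(24 + 12) = 11/36 = 30.6%.
- Phase 2, only referred borderline patients counted: 11/(24 + 2) = 11/26 = 42.3%.
- Apparent gain: 11.8 points.
- Referrals over all patients seen: 11/60 = 18.3% in both phases, so no gain.
- Referral hidden but phase known, with all borderline patients counted in Phase 1 and none in Phase 2: 11/36 = 30.6% against 9/24 = 37.5%, a gap of 6.9 points.

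**Step 4. Range (also assumed).** Let r be the true rate in both phases. In Phase 1 the eligible group is inflated by a share b of non-referred borderline patients, giving r/(1 + b). In Phase 2 a share b of the non-referred eligible patients is dropped, giving r/(1 − b(1 − r)).

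| r | b | Phase 1 | Phase 2 | Apparent rise (points) |
|---|---|---|---|---|
| 20% | 10% | 18.2% | 21.7% | 3.6 |
| 20% | 20% | 16.7% | 23.8% | 7.1 |
| 20% | 30% | 15.4% | 26.3% | 10.9 |
| 40% | 10% | 36.4% | 42.6% | 6.2 |
| 40% | 20% | 33.3% | 45.5% | 12.1 |
| 40% | 30% | 30.8% | 48.8% | 18.0 |

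The direction of misclassification was chosen to favour coaching in every row.

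**The case against.** The strongest reply is that the protocol describes no outcome-aware classification at all. Several points in it stand.

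- **Phase 1.** A reader might infer that the experts judge eligibility with referral status in front of them. The protocol does not say so; section 5.5 lists referral apart from the clinical items. What remains is that no order or separation is stated.
- **Phase 2.** A reader might infer that the pre-visit judgement shifts with the outcome, or that patients are formally re-judged at the end. The first is impossible for a referral made at the visit. The second is not stated, since the end-of-phase wording may mean a simple tally. What remains is that the text does not say which.
- **Size.** The 11.8 points need every borderline patient to fall the favourable way in both phases. The Phase 1 half of the example does not even depend on knowing who was referred. The raw referral count, which section 5.1 also compares, would stay at 11 and expose the artefact.
- **Masking.** Section 10.7 answers a form question about group assignment, so it is weak evidence on how eligibility is classified.
- **Nature of the study.** NCCN criteria are external, which confines judgement to borderline cases, and this is a single-site quality improvement pilot.

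Two replies do not succeed. A single coordinator gives consistent recording, but section 5.1 gives the eligibility measurement to the experts. De-identification hides who the patient is, not the phase or the referral. Nor is this only an analysis-plan detail: section 5.1 itself fixes who counts, from which data and when.

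**Conclusion.** The point holds as a cheap improvement, not as a demonstrated bias. The documents support three facts: the experts who coach also measure eligibility and referral in both phases; referral is reported among the eligible; and the Phase 2 eligibility count is placed at the end of the phase without saying whether it uses the pre-visit determination. Borderline patients could therefore be classified with knowledge of referral.

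No size follows from the protocol. The figures of 3.6 to 18.0 points, and the 11/36 against 11/26 example, rest wholly on assumed counts and on misclassification in the direction that favours coaching. They show that a few patients can matter at this sample size; they do not predict what would happen.

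**What to change.** Amend section 5.1 so that, in both phases:

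1. The coordinator distributes only the clinical items and the family history questionnaire, without referral or testing information.
2. The experts record met or not met for each patient on one written NCCN checklist, using the same data items in both phases.
3. The coordinator locks this record before linking referral and testing outcomes.
4. In Phase 2 the locked pre-visit record is the one counted at the end of the phase.
5. Referrals are also reported over all patients seen with the listed cancers. Section 5.4 already collects that number, and it does not depend on the eligibility judgement.

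**Cost.** A one-page checklist and a set order of data release, with no extra reader; the coordinator already receives, codes and distributes the packets. Information that arrives late is noted separately and does not change the classification used for analysis. The rule concerns counting only and says nothing about whom OMC should offer testing.

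**Limits.** The experts still know the phase, so a phase-driven difference such as the 6.9 points in the illustration is not prevented; the all-patients rate is the check on it. The questionnaire is optional and given on the day of the visit in Phase 1, but sent ahead by email in Phase 2. Its completeness may therefore still differ even with an identical item list.

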3 NON-UW RESEARCH SETTING

**Complete this section only if UW investigators and people named in the SUPPLEMENT:
Non-UW Individual Investigators will conduct research procedures outside of UW and Harborview**

3.1 Reason for locations. Describe the reason(s) for choosing the locations.

This is especially important when the research will occur in locations or with populations that may be vulnerable to exploitation. One of the three ethical principles the IRB must consider is justice: ensuring that reasonable, non-exploitative, and well-considered procedures are administered fairly, with a fair distribution of costs and potential benefits.

OMC is the ideal site for this research study because of its rural and underserved location, which can pose many obstacles to their patients in accessing genetic evaluations for the treatment of their cancers and for their family members. OMC is an affiliate site of SCCA and this partnership, in which SCCA will provide coaching to OMC providers, will facilitate a more open line of communication between the sites. OMC providers will have the resources to increase access to genetic counseling and testing to its patients as well as refer their patients with more complicated cases to SCCA for genetic consultation services

3.2 Local context. Culturally appropriate procedures and an understanding of local context are an important part of protecting subjects. Describe any site-specific cultural issues, customs, beliefs, or values that may affect the research, how it is conducted, or how consent is obtained or documented.

Examples: It would be culturally inappropriate in some international settings for a woman to be directly contacted by a male researcher; instead, the researcher may need to ask a male family member for permission before the woman can be approached. It may be appropriate to obtain permission from community leaders prior to obtaining consent from individual members of a group. In some distinct cultural groups, signing forms may not be the norm.

This federal site maintains an international list of human research standards and requirements:

<http://www.hhs.gov/ohrp/international/index.html>

N/A

3.3 Location-specific laws. Describe any local laws that may affect the research (especially the research design and consent procedures). The most common examples are laws about:

- **Specimens** – for example, some countries will not allow biospecimens to be taken out of the country.

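### Section 5.1 credits a genetic evaluation only at UWMC and the SCCA, so a change of referral destination alone could register as a coaching effect if some Phase 1 patients are seen elsewhere

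*Protocol*

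**What the plan says.** Section 5.1 of the protocol lists three counts for each phase: patients who met NCCN criteria, patients referred to genetic counseling, and "how many either had a test online or were seen at UWMC and the SCCA for a genetic evaluation". The third count has the same wording in Phase 1 and Phase 2. Its use is stated at the end of the Phase 2 description: "This data will then be compared with phase 1 data to measure the effectiveness of SCCA's coaching for OMC's providers".

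The care pathway differs between the phases:

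- **Phase 1:** "The first phase does not involve intervention; OMC will be following their existing processes". No referral destination is described.
- **Phase 2, NCCN-eligible patients:** "the oncology team at OMC would include in their initial visit workflow to discuss importance of cancer risk assessment and offer genetic testing".
- **Phase 2, complicated cases:** "For the patients with a more complicated history, the OMC team would offer a referral to the SCCA for a complete cancer risk assessment evaluation". Section 3.1 likewise expects OMC providers to be able to "refer their patients with more complicated cases to SCCA for genetic consultation services".

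Section 10.10 describes the results differently. Section 10.10.c says that completed genetics appointments will be tracked. Section 10.10.d says that providers will be told, after each phase, "the number of those patients who complete a genetics appointment". Neither names a site.

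**The concern.** The intervention is meant to affect where some patients are sent, and the visit part of the outcome credits only certain places. Using the same wording in both phases does not protect the comparison in that situation. A Phase 1 patient evaluated at another service is not counted as a visit. A similar patient sent to the SCCA in Phase 2 is counted. The recorded number could then rise with no additional patient evaluated.

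The stated purpose in section 1.5 is to increase access to genetic counseling and testing, not to increase use of one institution. The restricted sites are also those of the coaching institution and its partner, which makes the count harder to defend as evidence that coaching worked. In addition, 5.1 and 10.10 give two versions of what should be one measure, and a patient seen elsewhere is counted under one and not under the other.

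**Working it through.** The protocol section at issue states no baseline rate, effect size or expected share of evaluations at other services, so there is no planned figure to reproduce. The check is a comparison of the texts, followed by an illustration under stated assumptions.

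**Comparison of the texts**

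| Measure | Where | Site limit |
|---|---|---|
| Referred to genetic counseling | 5.1, both phases | None |
| Seen for a genetic evaluation | 5.1, both phases | UWMC and the SCCA |
| Completed genetics appointments | 10.10.c | None |
| Completed a genetics appointment | 10.10.d | None |

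**Illustration.** Three quantities are assumed:

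- p: the true share of patients evaluated, equal in both phases, so that coaching has no real effect;
- s: the share of Phase 1 evaluations that take place outside UWMC and the SCCA;
- r: the share of those outside evaluations that move to the SCCA in Phase 2.

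Patients seen elsewhere are assumed to have no online test, since such a test would count them anyway. Then:

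- recorded Phase 1 rate = p(1 − s)
- recorded Phase 2 rate = p(1 − s) + p·s·r
- apparent gain = p·s·r

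With p = 40% and every outside evaluation redirected (r = 1):

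- s = 0: 40% against 40%, gain 0 points
- s = 25%: 40% × 0.75 = 30% against 40%, gain 10 points
- s = 50%: 40% × 0.50 = 20% against 40%, gain 20 points

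These are upper cases for each s. With r = 0.5 they become 0, 5 and 10 points.

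In counts, take 60 patients per phase (the site maximum in section 2.7) and 20 true evaluations in each phase:

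| s | r | Phase 1 | Phase 2 | Apparent gain | Fisher exact p |
|---|---|---|---|---|---|
| 10% | 1 | 18 | 20 | 2/60 = 3.3 points | 0.85 |
| 25% | 1 | 15 | 20 | 5/60 = 8.3 points | 0.42 |
| 50% | 1 | 10 | 20 | 10/60 = 16.7 points | 0.057 |
| 50% | 0.5 | 10 | 15 | 5/60 = 8.3 points | not run |

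The p-values are only a yardstick for how such a shift would look at this size.

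**Any-site count.** If an evaluation anywhere is credited, the recorded rate is p in both phases and the apparent gain is 0 for every s and r, provided outside visits are found.

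**Direction.** Let m be the percentage points by which tests arranged at OMC but not credited as online tests are more common in Phase 2 than in Phase 1. The net error in the comparison is p·s·r − m. It favours coaching if p·s·r exceeds m and hides a real gain if m is larger. The documents give none of these quantities.

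**The case against.** The strongest objection is that the premise is undocumented. Nothing in the protocol says that OMC patients use other genetics services. OMC is an SCCA affiliate (section 3.1) and already sends records to SCCA oncologists for review (section 5.7.e). The Phase 1 sentence may simply list OMC's usual routes. If so, s = 0 and there is no artefact. This stands, and it makes the concern conditional.

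Other limits also stand. Only patients with a more complicated history are offered SCCA referral, and section 5.1 leaves providers free not to follow the coaching, so r is likely to be below 1. The affected item is one half of an either/or count, and the referral and NCCN-criteria counts compared beside it have no site limit.

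A reader might infer that the whole protocol recognises only UWMC and SCCA visits. It does not: section 10.10 is site-neutral. A reader might also infer that completion among referred patients is understated. Section 5.1 defines no such rate. Only 10.10.d nests completion within referral, and there a visit anywhere counts.

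These points reduce the likely size. They do not remove the restriction from the section that defines the comparison, or the mismatch with 10.10.

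**Conclusion.** The concern holds in conditional form. Section 5.1 restricts the evaluation count by site, section 10.10 does not, and the restricted count is among those compared to measure coaching. A shift in destination could therefore appear as a gain if some Phase 1 patients are evaluated at other services.

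The size is unknown. It is zero if there are no such patients. At an assumed true rate of 40%, it is at most 10 points at s = 25% and at most 20 points at s = 50%, and proportionately less where only some evaluations are redirected.

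It is tempting to conclude that the definition favours the intervention overall. The documents do not support that. Phase 2 has the OMC team offer testing itself, and it is unclear whether such a test falls under the online-test wording. If it does not, the same sentence would miss real Phase 2 gains, so the net direction is uncertain. The repair is worthwhile because it removes a possible artefact and reconciles two sections at little cost.

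**What to change.** In section 5.1, for both phases, replace the site-restricted visit wording with a completed genetics evaluation at any service, in person or remote, consistent with 10.10.c and 10.10.d. Add a field for where the evaluation took place. Compare the phases on the any-site count, and report the UWMC/SCCA share separately as a description. This does not settle the testing half of the count, so the same edit should say whether a test arranged at OMC is included.

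The cost is one wording change and one extra item in the chart abstraction that OMC already performs (section 5.5). The downside is that evaluations elsewhere are found only if they are documented in the OMC chart. Some may still be missed, and chart completeness could differ between phases.
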